9.3.4. Venous Clinical Severity Score (VCSS) – Pain Score

The VCSS system is a scoring system used to categorize nine attributes of venous disease into levels of severity ranging from 0 (absent) to 3 (severe). For this study, only the Pain Score will be collected.

Venous Clinical Severity Score (VCSS) – Pain Score		
Attribute	Score	Description
Pain (presumes venous origin)	Absent = 0	None
	Mild = 1	Occasional, not restricting activity or requiring analgesics
	Moderate = 2	Daily, moderate activity limitation, occasional analgesics
	Severe = 3	Daily, severe limiting activities or requiring regular use of analgesics

9.3.5. Villalta Score

The Villalta Scale for post thrombotic syndrome (PTS) is a scoring system in which five symptoms and six clinical signs are categorized by severity ranging from 0 (absent) to 3 (severe) as well as presence or absence of venous ulcer. A total score of 0 through 4 indicates no PTS, a score of 5 through 14 indicates mild/moderate PTS and a score of 15 or greater or presence of venous ulcers indicates severe PTS.

The Villalta Scale	
Symptoms	Score (Absent=0, Mild=1, Moderate=2, Severe=3)
Pain	
Cramps	
Heaviness	
Pruritus	
Paraesthesia	
Clinical Signs	Score (Absent=0, Mild=1, Moderate=2, Severe=3)
Pretibial edema	
Skin induration	
Hyperpigmentation	
Redness	
Venous ectasia	
Pain on calf compression	
Venous Ulcer	Present or Absent
Total Score*	

*The total score is the sum of all scores for each symptom and clinical sign. A score of 0 through 4 indicates no PTS, a score of 5 through 14 indicates mild/moderate PTS and a score of 15 or greater or presence of venous ulcers indicates severe PTS.

9.4. Questionnaires

9.4.1. **VENous INSufficiency Epidemiological and Economic Study Quality of Life/Symptoms (VEINES-QOL/Sym)**

The VEINES-QOL/Sym scale is a 26-item subject-reported measure that generates 2 separate summary scores for symptoms (VEINES-Sym) and quality of life (VEINES-QOL).

- The VEINES-QOL summary score (25 items) is an estimate of the disease effect on a subject's quality of life
- The VEINES-Sym summary score (10 items) measures the severity of physical symptoms.

This questionnaire must be completed by the subject. Responses are evaluated on a 2-point to 7-point scale that rates intensity, frequency, or agreement.

9.4.2. **EQ-5D-3L**

The EQ-5D-3L instrument includes five dimensions; mobility, self-care, usual activities, pain/discomfort, and anxiety/depression. They each have three levels of categorization. This questionnaire must be completed by the subject.

9.5. **Intravascular Ultrasound Imaging**

IVUS is a very important imaging modality used in conjunction with venography. To some, this is considered the new gold standard in venous imaging. IVUS allows for direct imaging of the vein from an inside-out vantage point with high resolution reproduction of the vessel lumen, vessel wall, and importantly, the extravascular structures in close proximity to the vein. This is particularly useful for detecting iliofemoral compression syndrome, often caused by overriding iliac arteries or mass-effect from other nearby structures (tumors, aneurysms, etc.). Intraluminal filling defects such as acute or chronic thrombus, webs, or spurs are better imaged and identified with IVUS. Additionally, accurate and reproducible direct measurements of vessel diameter (long and short axis) and cross-sectional areas can readily be obtained using IVUS. The typical technique is to insert the IVUS catheter through the lesion and then acquire images as the catheter is pulled back. IVUS runs generally should begin in a normal segment of the vessel cranial to the lesion of interest and terminate in a normal segment caudal to the lesion. It is important to perform a slow and steady pull back of the IVUS catheter.

An IVUS run of the IVC, CIV, EIV, and CFV must be acquired both pre-treatment and post-treatment. Images must be acquired in DICOM format directly from the IVUS equipment for core laboratory analysis.

IVUS is required at the index procedure, for any reinterventions, and if the 12-month site reported or core laboratory adjudicated DUS shows >50% stenosis or occlusion of the stented segment. In addition, IVUS may be required for the 24 or 36-month DUS shows >50% stenosis or occlusion of the stented segment **and** the subject is symptomatic requiring a reintervention. Operators will be trained on the IVUS protocol provided by the core laboratory. No test cases are required for IVUS. A comprehensive overview for IVUS acquisition requirements can be found in the core laboratory manual.

9.6. **Venographic Imaging**

Venography is an important modality for the assessment and treatment of iliofemoral compression syndrome. A lower extremity vein caudal to the lesion, typically the popliteal vein or mid femoral vein, is accessed and radiopaque iodinated contrast is injected. Images are then captured as the dye flows cranially under digital subtraction angiography (DSA). This allows for the assessment of stenosis of the veins from extrinsic compression/obstruction, and for the detection of acute thrombus and intrinsic vein defects (webbing, spurs, etc.). Angiographic images are typically acquired in the AP view. However, angulated views from the LAO or RAO projections are essential to add additional information about vessel narrowing or “pancaking”, especially when the stenosis is eccentric. This is also useful if the AP view does not demonstrate a narrowing of the vessel. A lack of dye in a venous segment usually represents an occlusion. In the presence of occlusion there are typically numerous collaterals clearly visualized on venography.

A full venographic run of the IVC, CIV, EIV, and CFV must be acquired both pre-treatment and post-treatment. For all venography runs, a radiopaque or marker pigtail catheter should be utilized. This allows for accurate lesion length determination by the core laboratory. Images must be acquired in DICOM format with and without DSA. Full venographic runs, not only still frames, are required for core laboratory assessment.

Full venographic assessment must include the femoral vein, iliac veins, renal veins, and IVC at the index procedure, for any reinterventions, and if the 12-month site reported or core lab adjudicated DUS shows >50% stenosis or occlusion of the stented segment. In addition, venography may be required for the 24 or 36-month DUS shows >50% stenosis or occlusion of the stented segment **and** the subject is symptomatic requiring a reintervention. Operators will be trained on the venography protocol provided by the core laboratory. No test cases are required for venography.

A comprehensive overview for abdominal venography acquisition requirements can be found in the core laboratory manual.

9.7. **Duplex Ultrasound Assessment**

Abdominal/pelvic venous DUS is accepted as an effective method for diagnosis and follow up of iliofemoral obstruction syndrome and DVT. DUS combines spectral Doppler technology in addition to B-mode imaging to allow visualization of blood flow pattern abnormalities within the Iliofemoral veins in the presence of DVT or obstruction. Increased velocities associated with lumen narrowing can be visualized with spectral and color Doppler. B-mode cross-sectional and longitudinal imaging of diameters can also assess obstruction and extrinsic compression. A lack of color fill and B-mode visualization of thrombus can indicate DVT.

B-Mode, Color Doppler, and Spectral Doppler are required at the target vessels: IVC, CIV, EIV, and CFV. Color and Spectral Doppler B-Mode diameters are required at the narrowest point (lesion) of the target vessel and at a normal reference level taken caudal to the lesion. Velocity measurements are required at the narrowest point (lesion) of the target vessel and at a normal reference level taken caudal to the lesion.

Abdominal Venous DUS is required at the 30-day, 6-month, 12-month, 24-month, and 36-month follow up visits. Operators will be trained on the DUS protocol provided by the core laboratory. Each site is required to submit a test DUS exam to the core laboratory prior to performing any study related DUS exams.

A comprehensive overview for DUS acquisition requirements can be found in the core laboratory manual.

9.8. **X-ray Assessment**

An X-ray assessment will be performed at the 12-month, 24-month, and 36-month follow-up visits to assess the DUO Stent(s)' implant integrity for all subjects in whom at least one DUO Stent was placed during the index procedure.

A comprehensive overview of procedural requirements for X-ray assessments can be found in the core laboratory manual.

In Europe, the only medical procedure that may be considered a deviation from routine medical care are the X-rays performed during the 12, 24, and 36-month follow-up visits. The X-rays are performed to assess stent fracture and migration rates.

10. SCREENING PROCEDURES

All subjects presenting to the institution with a suspected iliofemoral venous outflow obstruction will be screened for initial eligibility. A trained member of the research team shall perform a preliminary evaluation of the potential subject's medical history and screen for initial eligibility. Only assessments consistent with the institution's standard of care may be performed prior to obtaining a signed consent form. If during pre-screening, a subject is found to meet one or more exclusion criteria, or does not meet one or more inclusion criteria, the subject would be considered a pre-screen failure. The reason for pre-screen failure must be documented in the screening log and no further action is required.

If a subject is not a pre-screen failure, the subject is eligible to move forward with the screening and informed consent process. Qualified and trained research staff listed on the Site Delegation of Authority Log will approach the subject and initiate the informed consent process.

10.1. Obtaining Informed Consent

All sites shall comply with 21 CFR 50, provisions of International Conference on Harmonization (ICH) E6 Good Clinical Practices (GCPs), local institutional review board (IRB)/ethics committee (EC) policies and all applicable local regulations for obtaining informed consent. Prior to obtaining informed consent, the PI or designee will thoroughly explain the nature and purpose of the study to the subject. The PI or designee will document the informed consent process in the subject's source records and use the most current IRB/EC approved informed consent form (ICF) for each subject **prior** to any study-specific screening/baseline tests or procedures being performed. This does not include those procedures or tests that are completed in the normal course of the subject's non-study related care and that are done prior to undergoing the study procedure, but shall include previously performed tests that may need to be repeated to determine eligibility.

All subjects shall possess the ability to understand the information contained in the informed consent form. Subjects will have the study procedures explained in a manner as non-technical as possible, including the risks, benefits, and follow-up requirements. If the subject agrees to participate in this study, the subject will be required to sign and date the ICF. If a subject possesses the ability to understand the informed consent process and participation in study, but due to physical inability cannot sign the ICF, an impartial witness may sign the ICF on behalf of the subject. Non-English-speaking subjects may only be enrolled if they sign an IRB/EC approved and certified translated informed consent form that has been IRB/EC approved and is reflective of his/her spoken language.

Once all required parties have signed the ICF, the subject will receive a copy of their signed informed consent form for his/her records.

10.2. Screening Success and Failure Criteria

Final eligibility of a subject will be confirmed during the Index Procedure. Subjects must provide prior informed consent no greater than 30 days prior to the index procedure. If 30 days have passed since the subject signed an informed consent form, the subject should be re-consented. Every effort will be made to ensure subject eligibility prior to enrollment. If the subject meets all the inclusion criteria and none of the exclusion criteria after pre-enrollment angioplasty, the subject will be considered eligible for

enrollment. If at any point prior to or just after pre-enrollment angioplasty, but prior to the DUO stent system being advanced through the introducer sheath, an exclusion criterion is met and/or an inclusion criterion is not met, the subject will be deemed a screen failure. No further follow-up will be required for these subjects; however, the following details will be documented in the subject's source records:

- Documentation that the subject is a screen failure
- Documentation of the inclusion/exclusion criteria that was met and/or not met, with clarification provided as necessary

11. BASELINE EVALUATION

11.1. Baseline Assessments

The following assessments will be performed during baseline evaluation. These examinations and tests will be used both to screen for eligible subjects and to provide baseline information for those subjects who meet study criteria. All assessments must be completed no more than 30 days prior to the subject undergoing the index procedure, except for the urine or blood pregnancy test and the SARS-CoV-2 test and/or COVID-19 questionnaire.

The urine or blood pregnancy test is required for female subjects of childbearing potential and must be completed no more than 7 days prior to the index procedure. The SARS-CoV-2 test may be required (See Inclusion 17) and must be completed no more than 8 days prior to the index procedure. The result of both tests must be negative for the subject to be eligible for enrollment in this clinical trial. A COVID-19 questionnaire may be used in place of a SARS-CoV-2 Test under certain conditions. See **Section 9.2 SARS-CoV-2 Testing** for more details.

- Informed Consent
- SARS-CoV-2 Test, if required per Inclusion 17
- Assessment of Inclusion/Exclusion Criteria
- Demographic information and medical history including risk factors
- Brief physical examination
 - Including height and weight
- Serum Creatinine, eGFR, WBC, Platelet Count, Hemoglobin
- PT/INR (only if a subject is on chronic warfarin)
- aPTT (only if a subject is on chronic heparin)
- Urine or blood pregnancy test (required for females of childbearing potential only) within 7 days prior to index procedure
- Venous Ulcer Assessment
- CEAP Classification
- VCSS Pain Score
- Villalta Score
- VEINES-QOL/Sym Questionnaire
- EQ-5D-3L Questionnaire
- Review of Concomitant medications

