6.2. Secondary Efficacy Endpoints

- Subject symptom relief via VCSS pain score at 12 months
- Primary assisted patency at 12 months
 - Defined as freedom from DUS core laboratory adjudicated occlusion or stenosis $>50\%$ within the stented segment following a reintervention due to a $>50\%$ but $<100\%$ stenosis. If DUS shows $>50\%$ stenosis or occlusion, confirmation by diagnostic IVUS is required.
- Secondary patency at 12 months
 - Defined as freedom from DUS core laboratory adjudicated occlusion or stenosis $>50\%$ within the stented segment following a reintervention due to 100% occlusion. If DUS shows $>50\%$ stenosis or occlusion, confirmation by diagnostic IVUS is required.

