7. CLINICAL TRIAL DESIGN

This is a prospective, multi-center, single-arm, non-blinded clinical trial designed to investigate the safety and efficacy of the Vesper DUO Venous Stent System as compared to a pre-defined performance goal (PG) established from published, peer reviewed scientific literature related to stenting of iliofemoral venous outflow obstructions.

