7.2. Subject Population

Subjects with nonmalignant iliofemoral venous outflow obstruction presenting with nonthrombotic (NT), acute thrombotic (AT), or chronic postthrombotic (CPT) disease pathogenesis will be selected for study participation. At least 20% of the total population must be enrolled in each group. Subjects must meet all inclusion criteria and not meet any of the exclusion criteria to be enrolled in this clinical trial.

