7.4. Subject Selection

7.4.1. Inclusion Criteria

Subjects must meet all the following Inclusion Criteria. The response for each criterion below must be “Yes”:

1. Males or non-pregnant, non-breastfeeding females ≥ 18 years of age at the time of consent
2. Subject is able and willing to provide written informed consent prior to receiving any non-standard of care, protocol specific procedures
3. Female subjects of childbearing potential must have a negative pregnancy test within 7 days prior to treatment and must use some form of contraception (abstinence is acceptable) throughout the time of clinical trial exit
4. Willing and capable of complying with all required follow-up visits
5. Estimated life expectancy ≥ 1 year
6. Subject is ambulatory (use of assistive walking device such as a cane or walker is acceptable)
7. Body mass index (BMI) < 45

8. Clinically significant symptomatic venous outflow obstruction in one iliofemoral venous segment (one limb) per subject, is indicated for venoplasty and stenting, and meets at least one of the following clinical indicators:
 - a. CEAP score ≥ 3
 - b. VCSS pain score ≥ 2
 - c. Suspected deep vein thrombosis (DVT) with symptoms occurring prior to receiving a DUO Stent
9. Subject is willing and able to comply with PI recommendation for compression therapy, if required
10. Presence of unilateral, non-malignant venous obstruction of the common femoral vein (CFV), external iliac vein (EIV), common iliac vein (CIV), or any combination thereof, defined as a $\geq 50\%$ reduction in target vessel lumen diameter and confirmed by venographic or IVUS imaging. The cranial point of the obstruction may extend to the iliac vein confluence of the inferior vena cava (IVC) and the caudal point may be 2mm above either the inflow of the deep femoral (or profunda) or the lesser trochanter, whichever is most cranial
11. Obstructive lesion(s) able to be treated with continuous stent coverage
12. Adequate inflow to the target lesion(s) involving at least a patent femoral or deep femoral vein and a landing zone in the CFV free from significant disease requiring treatment
13. Reference vessel diameter is of adequate size to accommodate the appropriate size stent as measured by IVUS
14. All vessels from insertion site through target vessel can accommodate a 9F or 10F sheath, depending on the stent size used
15. Ability to cross interventional devices through target lesion(s)

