The evaluation for pooling analyses specified in **Section 19.6** will be completed. If there is missing data for the ITT subjects, the sensitivity to missing data analysis outlined in **Section 19.7** will be completed. Additionally, the primary statistical analysis will be conducted in the per protocol sample overall and in the SARS-CoV-2 negative subset.

19.12. **Subgroup Summaries for Primary Endpoints**

Summary statistics for the following subgroups will be summarized. The study was not powered to demonstrate the primary efficacy and safety endpoints within the subgroups and therefore it is not an expectation that the primary safety and efficacy endpoint will be statistically significant within the subgroups defined by disease etiologies (NT, AT, CPT), gender, age, race and ethnicity. Age subgroups are defined by dichotomizing at the median.

19.13. **Secondary and Observational Endpoints**

The secondary endpoints are listed in **Section 6.2** and the observational endpoints are listed in **Section 6.3** and are supportive in nature. Descriptive statistics will be calculated and may be provided in labeling if deemed informative for the user. Descriptive statistics for the purposes of labeling are defined as N, mean, standard deviation, median, interquartile range, minimum and maximum for continuous variables, and number and percent of observations for categorical variables.

Standard statistical methods will be used and include the Kaplan-Meier product limit method for time to event endpoints and the Wilcoxon signed rank test for changes from baseline for endpoints compared to baseline. Statistical significance will be defined as two-sided $\alpha < 0.05$. Two-sided 95% confidence intervals may be calculated for estimates. P-values and 95% confidence intervals are not intended for the labeling.

Safety and efficacy endpoints will be evaluated in the sample of subjects meeting the ITT and PP definition in both the SARS-CoV-2 negative subgroup and all subjects.

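### Subjects admitted on VCSS pain alone have the qualifying reading reused as their baseline, which biases the change in pain toward relief by an amount the documents do not let us fix

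*Combined protocol and SAP*

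**What the plan says.** - **Design (section 7).** The study is a "prospective, multi-center, single-arm, non-blinded clinical trial".
- **Entry (section 7.4.1, criterion 8).** A subject qualifies who "meets at least one of the following clinical indicators": CEAP of 3 or more, VCSS pain of 2 or more, or "Suspected deep vein thrombosis (DVT) with symptoms occurring prior to receiving a DUO Stent".
- **Dual use (section 11.1).** "These examinations and tests will be used both to screen for eligible subjects and to provide baseline information". The list that follows includes the VCSS pain score.
- **Timing (section 8.1).** VCSS pain has one scheduled pre-treatment reading, at Baseline, up to 30 days before the index procedure. The Index Procedure column has none.
- **Scale (section 9.3.4).** One item with four levels, 0 to 3.
- **Endpoint (section 6.2).** The first-listed secondary efficacy endpoint is "Subject symptom relief via VCSS pain score at 12 months". No threshold for relief is given. Section 6.3 adds change in the same score at 24 and 36 months as an observational endpoint.
- **Analysis (section 19.13).** The methods include "the Wilcoxon signed rank test for changes from baseline for endpoints compared to baseline", at two-sided 0.05. Secondary endpoints are supportive. Their descriptive statistics may go into labeling if judged informative; p-values and confidence intervals are not meant to.
- **Case mix (section 7.2).** "At least 20% of the total population must be enrolled in each group", the groups being nonthrombotic, acute thrombotic and chronic postthrombotic.

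**The concern.** A subject who meets criterion 8 only through pain is in the trial because one reading on a coarse scale came out at 2 or 3. Some such readings are high through reading error or a temporary bad spell. A second reading without treatment would on average be lower, unless the score were perfectly reproducible. Using the gating reading as baseline counts that fall as improvement, and a signed-rank test against zero cannot separate it from a treatment effect.

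Subjects who meet the CEAP or DVT indicator would have entered whatever their pain score. The cut-off does not select their baseline, even if their pain also happens to be 2 or more.

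At stake is how a supportive efficacy result is read, and a mean change that could appear in labeling. Withholding the p-value does not help there, because the mean itself is shifted.

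**Working it through.** **Inputs from the documents.** The plan gives no effect size, power or sample size for VCSS pain, so there is no stated figure to reproduce. The expected number evaluable at 12 months is 160 × (1 − 0.20) = 128 (section 19.3). It is stated for primary efficacy and assumed here for VCSS pain. The test is two-sided at 0.05, so 2.5% false positives are nominal in the direction of relief.

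**Inputs that must be assumed.** These are the correlation between two readings in the same untreated subject, the distribution of scores before selection, and the share s of subjects who qualify by pain alone.

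**Model.** Each subject has two latent normal values with correlation r and no true change, both cut into scores 0-3. A share s is kept only if the first score is 2 or more; the rest are not selected on pain. The signed-rank test is applied to 128 differences, with 600 simulated trials per setting. The simulation standard error is at most √(0.25/600) = 0.020, about 2 percentage points.

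**Step 1: mean shift.** If d is the expected fall in pain-only subjects, the whole-sample spurious fall is s × d.

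- Score distributions 25/30/30/15% and 15/25/35/25% (scores 0-3), r = 0.6-0.8: d = 0.20 to 0.47. The whole-sample fall runs from 0.2 × 0.20 = 0.04 to 0.6 × 0.47 = 0.28.
- A higher-pain distribution, 5/10/45/40%, same r: d = 0.08 to 0.14. The whole-sample fall runs from 0.2 × 0.08 = 0.016 to 0.6 × 0.14 = 0.084.
- Combined range: about 0.02 to 0.28 points.

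**Step 2: false relief.** For the 15/25/35/25% distribution, each cell gives mean change and the percentage of trials with a significant fall:

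| r | s = 0 | s = 25% | s = 50% | s = 75% |
|---|---|---|---|---|
| 0.6 | 0.00; 1.5% | −0.08; 12.0% | −0.17; 53.7% | −0.25; 91.8% |
| 0.7 | 0.00; 1.8% | −0.07; 13.7% | −0.14; 42.2% | −0.20; 82.5% |
| 0.8 | 0.00; 1.8% | −0.05; 10.7% | −0.10; 32.8% | −0.15; 64.0% |
| 0.9 | 0.00; 1.8% | −0.03; 8.5% | −0.06; 22.2% | −0.09; 41.8% |

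With r = 0.6-0.8 and s = 20-60%, false relief is about 8-94% under the two lower-pain distributions (repeat runs put the upper end at 90-94%) and about 5-22% under the higher-pain one. The combined range is about 5-94%.

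**Step 3: where the bias disappears.** At s = 0 the rate is nominal, 1.5-3% over all settings. Using a second pre-treatment reading, not used for eligibility, as baseline gives 1.3-4.2%, provided its error is independent of the screening reading. If the two errors are correlated at 0.7, false relief fell only from 29% to 11% in the setting checked.

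**The case against.** **Pain is not the gate.** Criterion 8 is an either-or rule, and at least 20% of subjects must be acute thrombotic, who can enter by DVT. A 60% pain-only share, with that 20% set aside, means 60/80 = 75% of the remaining subjects have CEAP below 3. Nothing in the documents suggests so high a share. This stands, and it is why the point is confined to pain-only subjects. The documents do not exclude a sizeable share either.

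**The size is assumed.** A range of 5-94% says little more than that the effect could be trivial or large. Criterion 8 draws on clinically significant symptomatic disease, which favors the higher-pain distribution and the lower figures. The VCSS levels also describe a pattern of pain and analgesic use, which averages out some daily variation. All this stands. The direction of the bias does not depend on these inputs.

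**The endpoint is supportive.** True. Section 19.4 rests study success on the two primary endpoints. Villalta, VEINES-QOL/Sym and EQ-5D-3L are also followed, and none is an entry threshold.

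**A single arm has this weakness anyway.** Partly true. Expectation in an unblinded trial and natural recovery remain whatever is done. This component differs because it can be isolated without a control arm.

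**A repeat reading on the procedure day could fail.** Section 10.2 makes a subject a screen failure if an inclusion criterion is found unmet before the stent system is advanced, and section 8.1 rechecks eligibility at the index procedure. The second reading could thus become a second gate. Taken close to screening, it would also share that reading's error. This stands and shapes the fix.

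**Conclusion.** The point holds for subjects who meet criterion 8 through VCSS pain alone. Their baseline is selected to be high, their change at 12, 24 and 36 months is biased toward relief, and section 19.13 has nothing to absorb it.

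Under the stated assumptions the whole-sample shift is about 0.02-0.28 points on the 0-3 scale, with false relief in about 5-94% of trials against 2.5%. These are conditional figures, not estimates for this trial. Reliability, score distribution and pain-only share are all missing from the documents.

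A reader might infer that regression to the mean by itself will produce a significant relief result. The documents do not support that: pain is one of three entry routes, and with a small pain-only share and a reproducible score the shift is only about 0.03 points. Nor does the point touch study success. The 94% figure comes from the unfavorable end of every assumption together.

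This is a worthwhile correction to a supportive endpoint, mainly because its mean change could appear in labeling.

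**What to change.** **In section 19.13:**
1. Report VCSS pain change at 12, 24 and 36 months separately for subjects who met CEAP of 3 or more or suspected DVT, and for those who qualified by pain alone.
2. Take the first group as the estimate free of this selection. Within it, show DVT subjects apart, because natural recovery of acute DVT pain is a separate bias.
3. Describe the pooled result as uncontrolled change from baseline, not as relief due to the device.

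Baseline CEAP and VCSS pain are already collected. Confirm that suspected DVT as a qualifying indicator can be read from the eligibility record; the eCRF layout is not in the documents.

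**Optional, for subjects not yet treated:** add a second pre-treatment VCSS pain reading on a different day from screening, use it as the baseline for change, and state in sections 10.2 and 11.1 that it is not used for eligibility. Add it to the section 8.1 schedule.

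**Cost.** The reporting change is SAP wording, with smaller subgroups and hence less precision. The optional reading adds one eCRF item and the logistics of a second day. Either way the reported improvement is likely to be slightly smaller.
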